1.0 Table of Contents

1.0	7
2.0	7
3.0	7
4.0	7
5.0	8
6.0	12
7.0	12
8.0	12
9.0	12
10.0	13
11.0	13
12.0	14
13.0	14
14.0	16
15.0	16
16.0	17
17.0	17
18.0	18
19.0	18
20.0	18
21.0	19
22.0	19
23.0	20
24.0	20

PROTOCOL TITLE: Prospective Randomized controlled study comparing liposomal bupivacaine to bupivacaine interscalene blocks for arthroscopic rotator cuff repair surgery

VERSION DATE: 8/5/11/2020

ABBREVIATIONS/DEFINITIONS

- LB/ liposomal bupivacaine
- RCR/rotator cuff repair
- QOR/Quality of Recovery
-

PROTOCOL TITLE: Prospective Randomized controlled study comparing liposomal bupivacaine to bupivacaine interscalene blocks for arthroscopic rotator cuff repair surgery

VERSION DATE: 8/5/2020

STUDY SUMMARY

Study Title	Prospective Randomized controlled study comparing liposomal bupivacaine to bupivacaine interscalene blocks for arthroscopic rotator cuff repair surgery
Study Design	Prospective randomized double blind study
Primary Objective	Total opioids in 72 hours
Secondary Objective(s)	Pain scores within 72 hours, QOR at 72 hours, Number of phone calls to surgeon, adverse events, time to discharge
Research Intervention(s)/Investigational Agents	Liposomal bupivacaine and bupivacaine vs bupivacaine
Scientific Assessment	HRPP facilitated scientific assessment
IND/IDE # (if applicable)	Study Medication has been approved for use in shoulder surgery April 6, 2018
IND/IDE Holder	n/a
Investigational Drug Services # (if applicable)	n/a
Study Population	Adult patients aged 18 and older who are undergoing arthroscopic rotator cuff repair surgery
Local Sample Size (number of participants recruited locally)	90

PROTOCOL TITLE: Prospective Randomized controlled study comparing liposomal bupivacaine to bupivacaine interscalene blocks for arthroscopic rotator cuff repair surgery

VERSION DATE: 8/5/2020

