4.0 Study Endpoints/Events/Outcomes

- 4.1 Primary Endpoint/Event/Outcome: To determine if LB plus bupivacaine in an interscalene block results in less opioid use over 72 hours compared to bupivacaine only for RCR surgery.
- 4.2 Secondary Endpoint(s)/Event(s)/Outcome(s):
 - To determine if LB plus bupivacaine in an interscalene block results in less pain over 72 hours as compared to bupivacaine only in an interscalene block for RCR surgery. Assessed via total pain scores
 - To determine if LB plus bupivacaine in an interscalene block results in improved QOR at 72 hours as compared to bupivacaine only in an interscalene block for RCR surgery. Assessed via QOR 15 patient survey.
 - To determine if LB plus bupivacaine in an interscalene block results in fewer phone calls to the surgeon within 72 hours as compared to bupivacaine only in an interscalene block for RCR surgery.
 - To determine if LB plus bupivacaine in an interscalene block hastens readiness for hospital discharge compared to bupivacaine only in an interscalene block for RCR surgery. Study Intervention(s)/Investigational Agent(s)
- 4.3 Description: LB is a long acting local anesthetic. It is liposome encapsulated bupivacaine which allows for prolonged release of bupivacaine over a 72

PROTOCOL TITLE: Prospective Randomized controlled study comparing liposomal bupivacaine to bupivacaine interscalene blocks for arthroscopic rotator cuff repair surgery

VERSION DATE: 8/5/2020

hour period. Bupivacaine is a medium acting local anesthetic which provides between 6 and 24 hours of analgesia when used in a peripheral nerve block. Both medications are standard of care for use in interscalene blocks here at the U of MN. Acetaminophen is a medication used to treat pain, gabapentin is a gabapentinoid which is used to treat postoperative pain.

4.4 Drug/Device Handling: The LB will be stored in a locked pyxis fridge in a box labeled study LB. It will be retrieved by the PI and sub I's for use in the interscalene blocks.

- The LB will be stored in a locked pyxis fridge in a box labeled Liposomal Bupivacaine. The anesthesiologists in charge of regional anesthesia the day the procedure will be informed will write the order for dispensing the medication and the block per standard of care. It will be retrieved by the PI and sub I's for use in the interscalene blocks.

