and given a copy of the consent form to evaluate prior to surgery. On the day of surgery, the research coordinator, research assistant or primary or sub investigators will determine if the patient has any questions so that they can be answered. After discussion with the person obtaining consent, consent will be obtained in the pre-operative area. Subjects interested in the study will be presented with consent and Health and Insurance Portability and Accountability Act (HIPAA) forms. The patient will review the forms with the surgeon, research staff, or anesthesiologist. Subjects will be reminded that participation is completely voluntary, and that they may stop participation at any time without question or penalty. The surgeon, research staff, or anesthesiologist will answer any questions that the subjects may have about the study. If the patient decides to participate, they will be asked to sign the consent and HIPAA forms. One copy will be saved for study records, and the subject will be provided with a copy of the forms for their own records. The patient will then have an opportunity to ask any questions of the surgeon regarding the treatment option that has been selected. All forms will be locked and stored in a file cabinet in the research department. Enrollment will proceed from July 2018 to July 2019. Enrolling consecutive patients will help reduce selection bias.

Assessments: Post-operatively patients will be evaluated at 2 and 6 hours post-operatively by a blinded research staff. This person will not be aware of the patient's mode of analgesia. The patients will be contacted via in person assessment or via telephone at 24, 48, and 72 hours +/- 5 hours. Patients will be asked to rate their pain on scale of 0-10. The amount of opioids used by the patient will be recorded as will any other adjuvant pain medication used. The time in phase 1 and phase 2 of PACU will be recorded. The patients will be asked at 72 hours post-injection if they would undergo interscalene block with their medication again or if they would opt for a different form of pain management. Patients will fill out a Quality of Recovery Survey at 72 hours and 14 days, and be assessed for block related complications at this time. All complications will be recorded including:

- Failure of the block
- Wound infections
- Subsequent procedures

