- Complications related to placement of the interscalene block including nerve injury, prolonged sensory loss greater than 3 days, prolonged arm weakness greater than 3 days
- Opioid related side effects of nausea and/or vomiting
- Local anesthetic toxicity as evidenced by seizures or cardiovascular collapse without other reasonable etiology

Patients will be asked in the daily phone call if they or their family contacted anyone (any health care professional) regarding their pain overnight and that will be documented.

All data will be recorded on the Clinical Diagnostic Sheet and will then be given to the research coordinator for manual data entry. Data collection will continue until POD #14. At that time study participation will be terminated. Should patients be re-admitted to the

PROTOCOL TITLE: Prospective Randomized controlled study comparing liposomal bupivacaine to bupivacaine interscalene blocks for arthroscopic rotator cuff repair surgery

VERSION DATE: 8/5/2020

hospital in the next two weeks (Up to POD #30) for pain, a notation will be made in study records.

An analysis of the total cost of analgesics will be tabulated at the conclusion of the study to determine the most cost effective treatment option as this will be added into the cost of hospitalization including the number of days each patient spent in the hospital.

Blinding Procedure: The research assistant in this study will be blinded to the method of analgesia for the patient. The research assistant will assess pain one time per day. This person will not be responsible for any clinical testing and will record all data in the protected database daily. They will not have any access to the patients' clinical records or chart. **Any questions from the patient will be referred to the on-call resident or staff on call.**

5.2

Describe:

- The interscalene block is standard of care for patients and would be performed regardless of patient's participation in the study. All patients still would get preoperative multimodal treatment as well as an opioid sparing anesthetic.
- Patients would be required to take a dose of acetaminophen 975 mg oral and gabapentin 300 mg oral prior to surgery. They would then be required to receive an interscalene block with either liposome bupivacaine and bupivacaine or bupivacaine. Intraoperatively they would be required to receive propofol, lidocaine, ondansetron, dexamethasone, and ketamine for induction of anesthesia.

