6.0 Data and Specimen Banking

- 6.1 *Storage and Access:* All study data will be stored on excel spreadsheets stored in Box. Only the PI and members of the research team will have access to the data.
- 6.2 *Data:* The data from this study will be collected both from Epic and directly from the patient. The data collected includes: demographic data, age, weight, ASA class, duration of surgery, length of stay in recovery room both phase 1 and 2, amount of opioids given intraoperatively and post-operatively, non-opioid pain medication, pain score (0-10) at 2, 6, 24, 48, and 72 hours, satisfaction with treatment, Quality of Recovery survey at 72 hours and 14 days, and any adverse events.
- 6.3 *Release/Sharing:* N/A

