17.0 Provisions to Monitor the Data to Ensure the Safety of Participants

17.1 Data Integrity Monitoring.

The PI, co-investigators, and research assistants will all have access to the study data stored in the University's Box storage system. All the research assistants have experience collecting pain scores and other relevant study information. The PI of the study will periodically review the study data to ensure accuracy and completeness of study data.

17.2 Data Safety Monitoring: The Department of Anesthesiology has established a Data and Safety Monitoring Committee consisting of several staff anesthesiologists which include persons who are board certified as pain specialists. Data will be transmitted in box to persons on the board on a monthly basis for review. If there are patterns of adverse events, the board will meet as needed and provide recommendations.

All safety data will be collected on a case report form and transferred into an excel spread sheet that will be stored in box. Also, all phone call data will be collected on a case report form and transferred into excel in box.

All data will be collected by research assistants on a daily basis. Subjects are monitored at several intervals on day of surgery and daily up to 72 hours. If the patient is discharged prior to 72 hours they will Who will review the data.

The data will be reviewed on a regular basis (weekly) by the PI and research staff. If there are consistent complications noted a meeting will be convened by the DSMB for recommendations.

The statistical tests for analyzing the safety data to determine whether harm is occurring.

The statistician uses R or SAS for analysis. Most likely a regression analysis will be performed to see which event is most likely the contributor for the

PROTOCOL TITLE: Prospective Randomized controlled study comparing liposomal bupivacaine to bupivacaine interscalene blocks for arthroscopic rotator cuff repair surgery

VERSION DATE: 8/5/2020

complications Also a chi-square analysis can be performed. All is very dependent on data variability.

A fatal or serious adverse event that is attributable to either the delivery or the study medication itself.

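### The contact question described in the protocol measures something other than the phone-call endpoint it is meant to supply

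*Combined protocol and SAP*

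**What the plan says.** The Study Summary lists among its secondary objectives "Number of phone calls to surgeon". Section 4.2 gives the comparison: whether the liposomal arm "results in fewer phone calls to the surgeon within 72 hours as compared to bupivacaine only". The unit is calls, the recipient is the surgeon and the window is 72 hours. Neither place limits the calls to pain or to night-time.

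Section 5.1 (Assessments) describes the collection. In the daily study call, patients are asked if they or a family member "contacted anyone (any health care professional) regarding their pain overnight", and the answer is to be documented. Those study contacts take place "at 24, 48, and 72 hours +/- 5 hours".

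Two other places might bear on the endpoint. Section 17.2 states that "all phone call data will be collected on a case report form and transferred into excel in box". Section 6.2 states that "The data from this study will be collected both from Epic and directly from the patient", and then lists variables, none of which is a phone call.

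**The concern.** The endpoint and the question differ in who was called, when, why and, as worded, in what is counted. The errors run in both directions: some calls to the surgeon go unrecorded, and some contacts that were not with the surgeon are recorded.

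The analysis plan would not catch this. Section 15.3 gives no rule for the endpoint; it says only that the statistician will receive the protocol and work from its objectives. A statistician who receives the answers to the Section 5.1 question and the label in Section 4.2 has nothing to show that the two are different quantities. A result on pain-related overnight contacts could then appear under the heading of calls to the surgeon.

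**Working it through.** The protocol gives no figure to reproduce here, so the check is a comparison of text, followed by two illustrations on assumed values.

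**1. Endpoint and question side by side**

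| Attribute | Endpoint (Study Summary, Section 4.2) | Question (Section 5.1) | Consequence |
|---|---|---|---|
| Recipient | Surgeon | Any health care professional | Contacts with others are included |
| Window | All 72 h | Overnight | Daytime calls are missed |
| Reason | Not restricted | Pain | Non-pain calls are missed |
| Unit | Number of calls | Whether contact occurred | Repeat calls are missed, if only yes or no is stored |

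The first three differences are on the face of the text. The fourth is an inference from the word if; the protocol does not state a response format.

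**2. Does another section supply the count?**

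- Section 5.1 (Treatment technique) lists what the 24, 48 and 72 h calls ask: complications, current pain score, opioid pills and non-opioid medication. Calls to the surgeon are not among them.
- The lists in Sections 5.2 and 6.2 contain no call variable. They may not be exhaustive, but they do not specify this one.
- Section 17.2 names no fields, and does not say whether phone-call data means patients' calls or the study's own follow-up calls.
- Section 5.1 (Blinding Procedure) gives the blinded assistant no access to the chart, so that person cannot check answers against recorded calls. The same paragraph refers patients' questions to on-call staff, and nothing says whether such a contact counts as a call to the surgeon.

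**3. Clock time (illustration)**

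The length of a night is not stated. Assume 8 to 12 h. Three nights then cover 3 × 8 = 24 h to 3 × 12 = 36 h, and 24/72 = 33% while 36/72 = 50%. This is a share of hours, not a share of calls missed.

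**4. Count against three yes/no answers (illustration)**

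Assume that each answer is stored as yes or no, covers a full 24 h and concerns the right recipient, and that calls follow a Poisson distribution with mean m per patient over 72 h. The expected sum of the three answers is 3 × (1 − exp(−m/3)).

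| Assumed m | Expected sum | Shortfall |
|---|---|---|
| 0.2 | 0.19 | 3% |
| 0.5 | 0.46 | 8% |
| 1.0 | 0.85 | 15% |
| 2.0 | 1.46 | 27% |

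The loss from the unit alone is small if calls are rare. The mismatches of recipient, window and reason come on top of it and cannot be sized from the documents.

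**The case against.** The strongest reply is that the protocol describes a prompt, not a form. The answer is to be documented, phone-call data go on a case report form, and Epic is a source. The form and the call script are not in the documents, and may well record recipient, number and time. This stands against the stronger conclusion that a reader might draw, that the endpoint cannot be computed. The documents do not show that. It does not answer the narrower point, because no section says that these items are recorded.

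A reader might also infer that the variable is capped at 3, with four possible values from 0 to 3, or that a third to a half of calls are captured. The cap depends on the inferred yes/no format. The percentages are clock hours under an assumed length of night, and they treat the first day as a full 24 h although part of it is spent in recovery before discharge. Neither is a finding about bias.

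Finally, the question may be the better idea and the endpoint label the mistake. Pain is the stated purpose in Section 2.0, and with questions routed to on-call staff, a question about the surgeon alone could miss relevant calls. That is a fair argument for changing the endpoint instead. It is not an argument for leaving the two different.

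**Conclusion.** Wrong as written: the collection item described does not match the phone-call endpoint. Recipient, window and reason differ on the plain text; the unit differs if the question is taken as worded. No other section reconciles them.

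The conclusion rests on the protocol text alone and would be narrowed by a form that records each call's recipient, number and time. No size of bias can be given, because the documents state no call rate. The consequence is confined to one of the five secondary objectives in the Study Summary. The primary endpoint and the sample size are not affected.

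**What to change.** Make the question and the endpoint agree, in one of two ways.

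- **Keep the endpoint and change the question.** At the existing 24, 48 and 72 h contacts, ask how many calls the patient or family made since discharge (first contact) or since the last study contact. Record for each whether it went to the surgeon or surgical on-call team, or to another professional, and whether it was about pain. State explicitly whether on-call staff count as the surgeon. Sum the surgeon calls over 72 h as the endpoint and report other contacts as supportive. Since the last contact may fall anywhere from 72 − 5 = 67 h to 72 + 5 = 77 h, note the date and time of each call or say how that window is handled.
- **Keep the question and change the endpoint.** Redefine it in the Study Summary and Section 4.2 as any pain-related contact with a health care professional over 72 h, and drop the restriction to overnight from the question.

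Either way, state in Section 15.3 whether the variable is analysed as a count or as a proportion.

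The cost is one reworded item in the call script and form, with no extra contact. Section 15.2 speaks of continuing enrolment, so some answers may already exist under the present wording. Those should be reported as pain-related overnight contacts, not as calls to the surgeon.

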6.0 Data and Specimen Banking

- 6.1 *Storage and Access:* All study data will be stored on excel spreadsheets stored in Box. Only the PI and members of the research team will have access to the data.
- 6.2 *Data:* The data from this study will be collected both from Epic and directly from the patient. The data collected includes: demographic data, age, weight, ASA class, duration of surgery, length of stay in recovery room both phase 1 and 2, amount of opioids given intraoperatively and post-operatively, non-opioid pain medication, pain score (0-10) at 2, 6, 24, 48, and 72 hours, satisfaction with treatment, Quality of Recovery survey at 72 hours and 14 days, and any adverse events.
- 6.3 *Release/Sharing:* N/A

7.0 Sharing of Results with Participants

Results will not be shared with participants.

8.0 Study Population

- 8.1 Inclusion Criteria: All adult patients aged greater than 18 years of age that are undergoing arthroscopic rotator cuff surgery
- 8.2 Exclusion Criteria: Patients with allergy to local anesthetics, daily use of opioids for more than 3 weeks prior to surgery, patient refusal, patient with coagulopathy, non-english speaking patients, patients who are currently pregnant, and those who do not have access to a telephone.
- 8.3 Screening: Patients will be screened at their preoperative visit either in the surgeon's office or pre assessment center.

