- In addition to the surveys used to measure subjective and objective outcome, other data will be collected during patient interviews including:
 - Demographic data
 - Age
 - Weight
 - ASA class
 - Duration of surgery
 - Pain Score at 2, and 6 hrs after surgery and once a day thereafter
 - Length of stay in recovery room both phase 1 and phase 2
 - Amount of opioids given intraoperatively and post-operatively
 - Satisfaction with treatment
 - Quality of recovery survey at 72 hours and 14 days
 - Non opioids used
 - Adverse events
 - Length of hospital stay

PROTOCOL TITLE: Prospective Randomized controlled study comparing liposomal bupivacaine to bupivacaine interscalene blocks for arthroscopic rotator cuff repair surgery

VERSION DATE: 8/5/2020

- 5.3 Study Duration: We anticipate the study to take from June 2018 to June 2019. Patients will be in the study for 14 days and then their chart monitored for up to 30 days post surgery. The data analysis should take one month after full enrollment of the study.
- 5.4 Individually Identifiable Health Information: This study involves the use of individually identifiable health information. Please see attached HIPAA authorization form.
- 5.5 Use of radiation: n/a
- 5.6 Use of Center for Magnetic Resonance Research: n/a

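### Preoperative opioid use short of the exclusion limit is allowed but not listed for collection, so the opioid primary outcome lacks its natural baseline covariate

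*Combined protocol and SAP*

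**What the plan says.** All references are to the combined protocol and SAP.

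- **Eligibility (8.1, 8.2).** Inclusion is "All adult patients aged greater than 18 years of age that are undergoing arthroscopic rotator cuff surgery", with no requirement to be opioid-naive. The only opioid exclusion is "daily use of opioids for more than 3 weeks prior to surgery".
- **Primary endpoint (4.1).** The question is whether the liposomal combination "results in less opioid use over 72 hours compared to bupivacaine only for RCR surgery".
- **Data lists (5.2, 6.2).** Section 6.2 begins "The data collected includes: demographic data, age, weight, ASA class, duration of surgery", and its opioid item is "amount of opioids given intraoperatively and post-operatively, non-opioid pain medication". Section 5.2 has the matching item "Amount of opioids given intraoperatively and post-operatively". Neither list names preoperative opioid use.
- **Sources and screening (6.2, 8.3).** "The data from this study will be collected both from Epic and directly from the patient". "Patients will be screened at their preoperative visit either in the surgeon's office or pre assessment center".
- **Allocation (5.1).** A web random number generator is consulted immediately before the block. No blocking or stratification is described.
- **Analysis (15.2, 15.3).** The target is 70 patients for an estimated 80% power, taken from another study. No model, test or covariate is given for the primary outcome.

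**The concern.** The exclusion shows that the protocol regards prior opioid use as relevant, but it removes only sustained daily users. The remaining patients may range from none to daily use for up to 3 weeks. Prior use is the baseline counterpart of 72-hour opioid consumption and a natural candidate to predict it. Age, weight and ASA class are to be recorded, but this item is not.

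Two things are at stake. First, outcome variation that a covariate could remove stays in the error term of a trial of only 70 patients. Second, with unstratified allocation the arms may differ by chance in the share of prior users. A dataset built from the listed items would not show this, so the baseline table could not report it and the analysis could not account for it.

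**Working it through.** **The plan's own figure.** The 70 patients and 80% power in 15.2 cannot be reproduced, because no effect size, SD, alpha or sidedness is stated. They can only be back-solved. With 1:1 allocation (35 per arm) and two-sided alpha 0.05, both assumed, the normal approximation gives a detectable difference of (1.960 + 0.842) × √(2/35) = 0.67 SD. With a t-test, 0.68 SD gives 80.1% power; 0.68 is used below.

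**Assumed inputs, none from the documents.** Prevalence of any prior use q = 10%, 20% or 30%. Prior users consume D = 0.5 or 1.0 SD more than non-users (SD within the user and non-user groups).

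**Step 1: variance explained and power gained.** R² = q(1−q)D² / (1 + q(1−q)D²). Adjustment raises the standardised effect to 0.68/√(1−R²). Power is from the two-sample t-test at 35 per arm.

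| q | D | R² | adjusted effect | power |
|---|---|---|---|---|
| 10% | 0.5 | 0.022 | 0.688 | 80.9% |
| 20% | 0.5 | 0.038 | 0.693 | 81.6% |
| 30% | 0.5 | 0.050 | 0.698 | 82.0% |
| 10% | 1.0 | 0.083 | 0.710 | 83.3% |
| 20% | 1.0 | 0.138 | 0.732 | 85.5% |
| 30% | 1.0 | 0.174 | 0.748 | 87.0% |

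Against 80.1% unadjusted, the gain is about 1 to 2 points at D = 0.5 and 3 to 7 points at D = 1.0. These figures use 68 error degrees of freedom. Fitting three covariates leaves 65 and changes power by less than 0.1 point.

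**Step 2: chance imbalance.** The number of prior users in each arm is taken as binomial (35, q). A difference of at least 15 points means 6 or more patients, because 5/35 = 14.3% and 6/35 = 17.1%. At least 10 points means 4 or more. Both directions are counted.

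| q | P(at least 10 points) | P(at least 15 points) | mean absolute difference |
|---|---|---|---|
| 10% | 16% | 2.8% | 5.6 points |
| 20% | 29% | 9.9% | 7.6 points |
| 30% | 36% | 15.1% | 8.7 points |

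**Step 3: what an imbalance does to the estimate.** Shift = imbalance × D. For 15 points this is 0.15 × 0.5 = 0.075 SD, or 0.15 × 1.0 = 0.15 SD. Simple division by 0.68 gives 11% and 22%. However, D is in within-group SD while 0.68 is in total SD. Dividing the shift by √(1 + q(1−q)D²) puts both on the total-SD scale and gives about 11% at D = 0.5 and 20% to 21% at D = 1.0.

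**The case against.** The strongest reply is that no validity problem exists. Under randomisation the unadjusted comparison is unbiased on average. Its standard error already contains the variation due to prior use, so type I error and interval coverage are not harmed. Section 8.2 also removes the sustained daily users, in whom the difference would probably be largest. All of this stands. A reader might infer that the primary result would be biased; the documents do not support that.

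A reader might also infer that adjustment is impossible. That is too strong. Section 6.2 names Epic as a source, both lists are worded as open-ended, and screening must establish opioid use to apply 8.2. The supportable statement is that the item is not listed for collection. Even so, a covariate retrieved after outcomes are known would be a post hoc choice, and non-daily use may not be charted reliably.

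A third temptation is to lead with a shift of about a fifth of the detectable effect. That needs the largest assumed association together with an imbalance that occurs in 3% to 15% of trials, counting both directions. The average imbalance is 5.6 to 8.7 points.

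Finally, 15.3 contains no primary model at all, and that is the larger gap. This is fair: the covariate needs a model to belong to, so the fix must supply both.

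**Conclusion.** The point holds as one of precision and transparency. Followed as written, the plan admits patients with some prior opioid use, must ask about it at screening, and does not list the answer for the dataset. The cost is modest: about 1 to 7 points of power forgone, and a chance imbalance on the factor closest to the endpoint that would go unreported.

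The size rests on assumed prevalence, association, alpha, allocation ratio and effect size, since the documents state none of these. If prior use is rare or only weakly related to 72-hour consumption, the gain is near the bottom of the range. The case for recording it does not depend on where in the range the truth lies, because without the field nobody will know. The change is worth making before analysis, but its absence would not invalidate the trial.

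**What to change.** 1. Add preoperative opioid use to the lists in 5.2 and 6.2, recorded at the screening visit and before randomisation. Epic can serve as a cross-check.
2. Write into 15.3 a primary model for 72-hour opioid use that adjusts for any prior use (yes/no), with age and weight, which are already collected.
3. Report prior use by arm in the baseline table.

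A yes/no term is preferable to finer levels. At 10% prevalence only about 0.10 × 70 = 7 patients would be users, too few to divide between non-daily and short daily use. More detail may be recorded for description.

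The cost is one extra data field, a primary model that has to be written down, and a few degrees of freedom. Eligibility, treatment and sample size are unchanged.
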